# 9.7.1 Blood Chemistry, Hematology, Pharmacokinetic and Response biomarker Samples

The chemistry, hematology and response biomarker parameters to be evaluated during the study are presented in Appendix 1. Detailed instructions regarding sample collection and processing are provided in the laboratory manual. Collection times are summarized in the Events Schedules (Section 5 and Section 9.6).

# 9.7.2 Urine Samples

The urine parameters, including SnPP urinary excretion, and response biomarkers to be evaluated during the Study are presented in Appendix 1. Detailed instructions regarding sample collection and processing are provided in the laboratory manual. Collection times are found in the Events Schedules (Section 5 and Section 9.6). All urine samples will be analyzed by the laboratory, except for urine pregnancy tests for women of childbearing potential.

All women of childbearing potential (defined as not surgically sterile nor postmenopausal for at least 2 years) will have a urine pregnancy test performed at the clinic as part of the screening procedure prior to any investigational product administration and at an End of Study using the pregnancy kit supplied by the laboratory.

Protocol Number: REN-003 (Original)

Date: 25 March 2019

### 9.8 Clinical Procedures and Observations

The research clinic will follow its own standard operating procedures for the daily ongoing monitoring of subjects while subjects are in the clinic (e.g. pulse, O2 saturation, etc.). Subjects will be monitored for any adverse events occurring at any time throughout the study.

#### 9.8.1 ECG

ECGs will utilize a 12-lead recording. Collection times are summarized in the Events Schedules (Section 5 and Section 9.6). ECG results will be assessed by the investigator/sub-investigator.

# 9.8.2 Concomitant Medications

All concomitant medications taken by the subject from 30 days prior to Study Day 1 through the end of study (28 [ $\pm$  1] days after the dose of investigational product) will be recorded.

### 9.8.3 Physical Examination

A full physical examination, including height (Study Day 1 only) and weight (weighed on the same scale in the same state of dress), will be conducted at Day 1 and at end of the study. Collection times are summarized in the Events Schedules (Section 5 and Section 9.6).

All physical examinations are to be performed by the investigator/sub-investigator or designee whose license permits the performing of physical examinations.

### 9.8.4 Vital Signs

Blood pressure (systolic and diastolic), pulse, and body temperature will be measured before investigational product is administered and after the subject has been in a sitting position for  $\geq 5$  minutes. Collection times are summarized in the Events Schedules (Section 5 and Section 9.6).

#### 9.8.5 Meals and Dose Administration

There are no dietary restrictions in this study. Subjects should continue to eat their normal diet. Breakfast may be eaten before or after the infusion of SnPP on Study Day 1.

#### 9.8.6 Prohibited Medications

Medications which can cause photosensitivity are prohibited for subjects in the Study.

Oral iron medication may be taken prior to screening but must be discontinued upon enrollment.

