#### **Exclusion Criteria:**

- 1. History of malignancy except carcinoma in situ in the cervix, early stage prostate cancer or non-melanoma skin cancers. Cancer free for less than 5 years.
- 2. Use of investigational drugs or participation in another clinical trial within 30 days or 5 half-lives prior to screening, whichever is longer.
- 3. Serum ferritin > 500 ng/ml or who have received IV iron within 28 days of screening, or currently being treated with oral iron.
- 4. Women who are pregnant, breastfeeding, or planning to become pregnant while participating in the study.
- 5. Regular use of drugs of abuse and/or positive findings on urinary drug screening.
- 6. Current tobacco use and/or positive findings on urinary cotinine screening.
- 7. Subjects who are severely physically or mentally incapacitated and who, in the opinion of investigator, are unable to perform the subjects' tasks associated with the protocol.
- 8. Presence of any condition which, in the opinion of the investigator, places the subject at undue risk or potentially jeopardizes the quality of the data to be generated.
- 9. Subjects with history of photosensitivity or active skin disease, which, in the opinion of the investigator could increase the risk of photosensitivity.
- 10. Subjects with abnormal baseline liver tests or hepatitis serologies that suggest active infection
- 11. Subjects with CKD and not at their baseline of renal function and have significant acute or chronic illnesses.
- 12. Known hypersensitivity or previous anaphylaxis to SnPP or to components thereof.

Protocol Number: REN-003 (Original)

Date: 25 March 2019

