- Haptoglobin, Ferritin, Bilirubin, Hemopexin, IL-10, P21 and HO-1.
-  Cystatin-C, IL-6, SnPP, total porphyrin, Tin, Troponin I, albuminuria, Kidney Injury Molecule-1 (KIM-1), Neutrophil Gelatinase-Associated Lipocalin (NGAL), N acetyl-beta-D-glucosaminidase (NAG), (in addition to BUN/Cr which are part of the Serum Chemistry panel)
- Three measurements will be taken for the urinary safety biomarkers (albuminuria, Kidney Injury Molecule-1 (KIM-1), Neutrophil Gelatinase-Associated Lipocalin (NGAL), and N acetyl-beta-D-glucosaminidase (NAG)), eGFR, and response biomarkers prior to dosing.
- \*\* Day 14 safety evaluation will be conducted at the request of the DSMB after each cohort safety review

Protocol Number: REN-003 (Original)

Date: 25 March 2019

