#### 9.2.2 CKD Exclusion Criteria

- 1. History of malignancy except carcinoma in situ in the cervix, early stage prostate cancer or non-melanoma skin cancers. Cancer free for less than 5 years.
- 2. Use of investigational drugs or participation in another clinical trial within 30 days or 5 half-lives prior to screening, whichever is longer.
- 3. Serum ferritin > 500 ng/ml or who have received IV iron within 28 days of screening.
- 4. Women who are pregnant, breastfeeding, or planning to become pregnant while participating in the study.
- 5. Regular use of drugs of abuse and/or positive findings on urinary drug screening.
- 6. Current tobacco use and/or positive findings on urinary cotinine screening.
- 7. Subjects who are severely physically or mentally incapacitated and who, in the opinion of investigator, are unable to perform the subjects' tasks associated with the protocol
- 8. Presence of any condition which, in the opinion of the investigator, places the subject at undue risk or potentially jeopardizes the quality of the data to be generated.
- 9. Subjects with abnormal baseline liver tests or hepatitis serologies that suggest active infection.
- 10. Subjects with CKD and not at their baseline of renal function and have significant acute or chronic illnesses.
- 11. Subjects with history of photosensitivity or active skin disease
- 12. Known hypersensitivity or previous anaphylaxis to SnPP.

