# 9.6.2 Screening (Within 14 Days Prior to Study Day 1)

- 1. Subjects will arrive at the clinical testing unit in the morning after fasting (defined as nothing by mouth except water) for at least 8 hours prior to the collection of any blood samples.
- 2. Eligibility will be confirmed.
- 3. Demographic characteristics and medical history will be obtained.
- 4. Physical examination (including height and weight), vital signs (after sitting  $\geq 5$  minutes), and 12-lead ECG (after sitting  $\geq 5$  minutes) will be performed.

Protocol Number: REN-003 (Original)

Date: 25 March 2019

5. Blood and urine will be collected for clinical laboratory tests (Appendix 1) and drug/alcohol/cotinine screen.

- 6. For women of childbearing potential, urine pregnancy test will be performed.
- 7. Eligible subjects will return to the clinical testing unit within 14 days for confinement and dosing.
- 8. An additional blood and urine sample will be taken between screening and prior to dosing on Study Day 1 in order to establish a baseline measurement for safety and efficacy biomarkers (a total of three measurements).

# 9.6.3 Study Day 1

- 1. Subjects will arrive at the clinic at 8:00am ( $\pm 60$  minutes).
- 2. All eligibility criteria will be assessed.

For CKD subjects, subjects whose GFR value does not meet the inclusion criteria may be re-screened 2 more times during the trial. If the ICF has been signed within 30 days and there are no new revisions, a new ICF is not necessary. If a subject is re-screened, the subject will be given a new screening number in the eCRF system and source documents.

- 3. If all eligibility criteria are met, the following Baseline samples will be collected (Appendix 1):
  - Blood samples for standard assessment of hematology and serum chemistry.
  - Blood samples for measurement of response biomarkers (Haptoglobin, Ferritin, Bilirubin, Hemopexin, IL-10, P21 and HO-1).
  - Blood samples for measurement of Safety biomarkers (Tin, Total Porphyrins, IL-6, Troponin I and Cystatin-C).
  - Blood samples for measurement of SnPP.
  - Urine for standard assessment of urinalysis parameters and safety biomarkers (albuminuria, Cystatin-C, Kidney Injury Molecule-1 (KIM-1), Neutrophil Gelatinase-Associated Lipocalin (NGAL), and NAG).

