  - Urine samples for measurement of response biomarkers (Hemopexin, Ferritin, P 21 and HO-1), and for urinary clearance of SnPP. Urine samples will be collected and centrifuged and analyzed for subject responsiveness to SnPP therapy.
- 2. A Baseline ECG will be performed (Section 9.8.1).
- 3. A full physical examination including height, weight, and vital signs will be performed (Sections 9.8.3 and 9.8.4).
- 4. Medical history and prior/concomitant medication information will be collected. (Section 9.8.2)
- 5. Subjects who meet all inclusion/exclusion criteria will be enrolled into the Study and the following procedures will take place:
  - The dose of SnPP will be administered in the clinic as a "push," direct infusion over a  $120 \pm 5$ -minute period. Food may be given after the infusion.

Date: 25 March 2019

Observe for signs and symptoms of hypersensitivity during and after administration for at least 30 minutes and until clinically stable following completion of each administration. Only administer when personnel and therapies are immediately available for the treatment of serious hypersensitivity reactions.

Should a subject experience nausea during or after infusion, the investigator may order Ondansetron (Zofran®) per its label instructions. Zofran may also be given prophylactically if at lower doses nausea is observed in subjects.

- Patients will be advised on other interventions necessary to mitigate the risk of phototoxicity such as wearing a hat, sunglasses, long sleeve shirts and sunscreen with an SPF≥30, when appropriate,.
- A post-infusion ECG will be performed 10 minutes (± 15 minutes) after the end of the infusion.
- The clinic staff will solicit any adverse events.
- Response biomarker samples will be collected at 2, 4, 8, 12, and 18 hours ( $\pm$  15 minutes) after the start of the infusion.
- Blood samples for pharmacokinetic analysis will be collected at 1, 2, 3, 4, 6, 8, 12, 18 and 24 hours (± 15 minutes) after the start of the infusion.
- Lunch and dinner will be provided by the clinic.

# 9.6.4 Study Day 2

The following procedures will be done at 24 hours (± 15 minutes) after dosing:

- 1. Blood samples for standard assessment of clinical chemistry, hematology, and safety and response biomarkers will be collected (Appendix 1).
- 2. Blood samples for pharmacokinetic analysis will be collected.
- 3. Urine samples for standard assessment of urinalysis parameters and response biomarkers will be collected (Appendix 1).

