5 DEFINITIONS

Terminology	Definitions
Enrolled	Subjects who signed the informed consent, meet all inclusion criterian and none of the exclusion criteria are entered into the study
Completer	Subjects who complete the End of Study (EOS) visit
Study Day	Day 1 is defined as the date subject took the study medication. Study Day for event post Day 1 is calculated as Event Date – Day 1 Date +1. Study Day for event prior to Day 1 is calculated as Event Date – Day 1 Date. Note: There is no Day 0.
Baseline	Baseline is defined as the non-missing value collected most recent to and before the study of the study medication infusion
Prior Medication	Medication started and ended prior to the study drug infusion
Concomitant Medication	Medication taken on/after the study drug infusion. Concomitant medication may start prior to study drug infusion
Treatment-emergent Adverse Event	Adverse event with onset date/time on or after the start of study drug infusion.

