12 LIST OF TABLES

Note, all tables will be repeated for CKD Patients Population and Healthy Subjects Population with Table numbers.

CliniOps

**STATISTICAL ANALYSIS
PLAN (AMENDMENT # 1) of
REN003**

Version 1.0

***Enabling end-to-end eSourcing,
Monitoring & Patient Engagement***

**STATEMENT OF CONFIDENTIALITY /
DISCLAIMER**

This document is the property of ClinOps, Inc. No part of this document shall be reproduced, stored in a retrieval system, or transmitted by any means, electronic, mechanical, photocopying, recording, or otherwise, without prior written permission from ClinOps, Inc.

CliniOps, Inc.
Fremont, CA, USA
[contact]
www.cliniops.com

1. STATISTICAL ANALYSIS PLAN DETAIL.....	3
2. PURPOSE OF AMENDMENT.....	3
3. AMENDMENT CHECKLIST	3
4. SIGNATURE	4

1. Statistical Analysis Plan Detail

Client Name:	Renibus Therapeutics, Inc.
Study Name:	A Phase 1b dose-escalating study with Stannous Protoporphyrin (SnPP), in healthy volunteers and subjects with chronic kidney disease stage 3-4
Protocol:	REN003
Protocol No.:	IND 138109
Protocol Date/Version:	25 March 2019
IND No.:	138109
Study Phase:	1b
Study Drug:	SnPP
Statistical Analysis Plan Date/Version	28 July 2019 Version.1.0
Prepared by:	[name], MS
Sponsor:	Renibus Therapeutics, Inc. [name] [contact]

2. Purpose of Amendment

The purpose of this amendment is to adjust the section on the SAP to reflect the following changes:

- Define the baseline

3. Amendment Checklist

1. UPDATE the table in “SECTION 5: DEFINITIONS” to reflect the updated definition of ‘Baseline’:

Terminology	Definitions
Enrolled	Subjects who signed the informed consent, meet all inclusion criterian and none of the exclusion criteria are entered into the study
Completer	Subjects who complete the End of Study (EOS) visit

Terminology	Definitions
Study Day	Day 1 is defined as the date subject took the study medication. Study Day for event post Day 1 is calculated as Event Date – Day 1 Date +1. Study Day for event prior to Day 1 is calculated as Event Date – Day 1 Date. Note: There is no Day 0.
Baseline	Baseline is defined as the mean of three values from screening, study day -1 (one day before study day) and study day 1 prior to dosing
Prior Medication	Medication started and ended prior to the study drug infusion
Concomitant Medication	Medication taken on/after the study drug infusion. Concomitant medication may start prior to study drug infusion

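### CKD eligibility rules on oral iron conflict, and one reading lets iron stop only after the baseline ferritin samples

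*Protocol*

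**What the plan says.** Three places in the protocol bear on oral iron in CKD subjects.

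- **Synopsis, CKD exclusion 3.** After the ferritin and IV iron limits it adds "or currently being treated with oral iron".
- **Section 9.2.2, CKD exclusion 3.** The criterion is only "Serum ferritin > 500 ng/ml or who have received IV iron within 28 days of screening". No other item in that list mentions oral iron.
- **Section 9.8.6.** "Oral iron medication may be taken prior to screening but must be discontinued upon enrollment". The sentence is not limited to one population.

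Three others fix the timing.

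- **Section 9.6.3, Study Day 1.** Sampling comes first: "If all eligibility criteria are met, the following Baseline samples will be collected (Appendix 1"). Enrolment is a later item, directly before the infusion: "Subjects who meet all inclusion/exclusion criteria will be enrolled into the Study and the following procedures will take place".
- **SAP Section 5.** Enrolled subjects are "Subjects who signed the informed consent, meet all inclusion criterian and none of the exclusion criteria are entered into the study". No time point is attached.
- **Baseline.** Footnote 13 of the protocol's event schedule calls for three measurements of the urinary safety biomarkers, "eGFR, and response biomarkers prior to dosing". SAP Amendment 1 turns these into the analysis baseline: "Baseline is defined as the mean of three values from screening, study day -1 (one day before study day) and study day 1", the last of them before dosing.

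**The concern.** Who may enter depends on which part of the protocol a site follows. A site working from Section 9 can enrol a CKD subject whom the synopsis excludes, and nothing in either document says which version prevails. The SAP supersedes the protocol on statistical methods only.

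Ferritin is listed in the synopsis as a key parameter, and Section 9.5 makes the study open-label SnPP for everyone. The ferritin change from baseline therefore has no untreated comparison. If a subject takes oral iron through the baseline samples and stops at enrolment, the within-group change may mix iron withdrawal with any SnPP effect. SAP Section 7.6.1 reports that change as a least squares mean per dose level.

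The sponsor already treats iron exposure as relevant: exclusion 3 limits both serum ferritin and recent IV iron.

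**Working it through.** **1. The three rules side by side**

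| Place | Current oral iron user with CKD |
|---|---|
| Synopsis, exclusion 3 | Excluded |
| Section 9.2.2, exclusion 3 | Not excluded |
| Section 9.8.6 | Unclear: past use only, or use until enrolment |

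The first two rows conflict on any reading. The third does not settle the matter. If it means past use only, it agrees with the synopsis, but for CKD subjects the instruction to stop at enrolment then has almost nobody to act on. If it admits users who stop at enrolment, it agrees with Section 9.2.2 and contradicts the synopsis.

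**2. Timeline on the second reading**

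Screening sample, second pre-dose sample, Day 1 pre-dose sample, enrolment, infusion, then samples at 2 to 168 hours. All three baseline values come before enrolment, and nothing requires iron to have stopped by then. Every post-dose value comes after the stop. Day 1 does begin with an eligibility check ahead of the baseline samples, but a site using the Section 9.2.2 list would find no oral iron criterion to check.

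**3. How much of the analysis is touched**

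SAP Section 4 lists 7 blood and 4 urine response markers, 7 + 4 = 11 measures. Ferritin is 2 of them (blood and urine).

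**4. Weight of one user in a mean**

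- CKD model, per dose: 6 (stage 3) + 6 (stage 4) = 12, so 1/12 = 8.3%.
- Pooled model at 27 or 90 mg: 6 (healthy) + 12 (CKD) = 18, so 1/18 = 5.6%.

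**5. Illustration of scale**

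The documents give no figure for the number of users or for the effect of stopping oral iron on ferritin over 168 hours. Purely as assumptions, let *d* be the shift in a user's ferritin change, 2 to 20 points in either direction, and *k* the number of users at a dose, 1 to 3. With complete data and before covariate adjustment, the dose-group mean moves by *d* × *k* / *n*.

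| Model | k = 1 | k = 3 |
|---|---|---|
| CKD, n = 12 | 2/12 to 20/12 = 0.17 to 1.67 | 6/12 to 60/12 = 0.50 to 5.00 |
| Pooled, n = 18 | 2/18 to 20/18 = 0.11 to 1.11 | 6/18 to 60/18 = 0.33 to 3.33 |

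With *k* = 0 the shift is zero.

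**6. Reach of the medication record**

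Section 9.8.2 records medications from 30 days before Day 1. Screening is at most 14 days before Day 1. The record therefore reaches at least 30 − 14 = 16 days before the first baseline sample.

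**The case against.** The strongest reply concerns the wording of Section 9.8.6. Its permission covers oral iron only before screening, and screening supplies the first baseline value. On its words, then, the permission ends before baseline begins, and a site applying all three places together would exclude current users. This is a fair reading, but it makes the second half of the sentence nearly idle, so the ambiguity stands. It also leaves the mismatch between the synopsis and Section 9.2.2 untouched.

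Second, the bias has no documentary size. The shares 1/12 and 1/18 are the weight of any single subject, the 2 to 20 points are assumed, and the SAP's least squares means are adjusted for baseline, which the simple formula is not. All of that is right. The figures show scale only and do not estimate bias.

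Third, the planned contrasts are between doses. An iron effect enters the 90 versus 27 mg comparison only through chance imbalance in the number of users. That also stands: the exposure is in the uncontrolled within-group change, for 2 of 11 measures.

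Fourth, stopping iron before screening does not by itself remove a withdrawal trend in someone who stopped the day before. This is correct, and is why the washout needs a clinical decision and a sensitivity analysis is worth having.

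**Conclusion.** The concern holds. That the CKD eligibility rules conflict is certain from the text and rests on no assumption about effect size. The consequence for ferritin is conditional. It needs a site to follow Section 9 and the wider reading of Section 9.8.6, at least one subject who stops oral iron at enrolment, and a ferritin response to that stop within 168 hours. The documents establish neither the size nor the direction of such a response, and it may be small. One user would carry 8.3% of a CKD dose-group mean and 5.6% of a pooled mean at 27 or 90 mg. The other nine response measures are not in question. The correction should be made because the inconsistency decides who enters, a key marker is exposed without a control group, and the remedy is cheap.

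**What to change.** 1. Add the synopsis clause ("or currently being treated with oral iron") to exclusion 3 in Section 9.2.2.
2. Amend Section 9.8.6 so that oral iron must have stopped before the first baseline (screening) sample and stays off through the 168-hour sample, with any minimum washout set on clinical grounds. As that section applies to all subjects, this also covers healthy volunteers, whose exclusion lists do not mention oral iron.
3. Optional, in the SAP: flag any subject with recorded oral iron between 30 days before Day 1 and the 168-hour sample, and repeat the ferritin analyses without them as a sensitivity analysis. This also finds subjects who stopped shortly before screening, though not those who stopped before the record begins. It remains possible even if enrolment is complete.

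The cost is two protocol sentences, aligned to a rule the sponsor already wrote, with IRB approval of the amendment where Section 14.3 requires it, plus one flag and one repeat run if the optional step is taken. Eligibility becomes slightly tighter; by how much is unknown, since the number of users is not given. Groups are smaller in that one sensitivity analysis.

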# 10 ADVERSE EVENT REPORTING

All adverse events will be recorded on the designated study eCRF for each subject beginning with the first administration of investigational product and ending with the date of the end of study treatment follow-up. Any unresolved adverse events will be followed by the investigator until event resolution, the subject is lost to follow-up, the adverse event is otherwise explained or not considered clinically significant by the investigator.

